Trial endpoints	
The primary endpoint is the change from baseline in log transformed Urine Albumin Creatinine Ratio (UACR) measured in First Morning Void urine after 14 weeks.
 
Secondary endpoints:
 
UACR response I, defined as a decrease of at least 30% absolute change in First Morning Void urine of UACR from baseline to 14 weeks.
 
UACR response II, defined as a decrease of at least 15% absolute change in First Morning Void urine of UACR from baseline to 14 weeks
Trial design	Randomised, double-blind, parallel dose group, placebo-controlled clinical trial to investigate the effect of three doses of BI 690517 alone and in combination with empagliflozin over 14 weeks in

	patients with diabetic and non-diabetic chronic kidney disease. The trial will include a 1:1 randomised run-in period of 8 weeks for empagliflozin 10 mg/ placebo followed by a randomised treatment period of 14 weeks for BI 690517 / placebo in combination with the background medication assigned in the randomised run-in period.
Total number of patients randomised	At least, 552
Number of patients per treatment group	A minimum of 60 patients completed per arm in the Treatment Period, overall 480 completed patients
Diagnosis	Diabetic or non-diabetic Chronic Kidney Disease
Main inclusion and exclusion criteria	
Inclusion:
 
 • Male or female patients of legal adult age (according to local legislation) and aged ≥ 18 years at time of consent. • eGFR ≥ 30 and < 90 mL/min/1.73 m². • UACR ≥ 200 and < 5000 mg/g. • Stable treatment with either ACEi or ARB (not both). • Serum potassium ≤ 4.8 mmol/L 
Exclusion:
 
 • Current or planned SGLT2i / SGLT-1/2i treatment • Type 1 Diabetes Mellitus
Test product(s)	BI 690517 and empagliflozin
dose	BI 690517 3 mg daily (QD) or 10 mg daily (QD) or 20 mg daily (QD) Empagliflozin 10 mg daily (QD)
mode of administration	p.o
Comparator product(s)	Placebo matching each dose of BI 690517 and empagliflozin
dose	Not applicable
mode of administration	p.o.
Duration of treatment	22 weeks (8 weeks run-in with empagliflozin/placebo and 14 weeks of treatment with BI 690517/placebo alone or in combination with empagliflozin/ placebo)

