3.3 SELECTION OF TRIAL POPULATION

It is expected that at least 552 patients will be randomised to the Randomised Run-in Period from approximately 200 sites. Investigators are expected to be nephrologists, endocrinologists or general practitioners. Screening of patients for this trial is competitive, i.e. screening for the trial will stop at all sites at the same time once a sufficient number of patients has been screened. Investigators will be notified about screening completion and will then not be allowed to screen additional patients for this trial. Patients already in screening at this time will be allowed to continue to randomisation if eligible.

A minimum of 552 patients will be randomised to the Run-in Period to ensure that at least 480 will complete the study treatment in order to preserve the trial power by increasing sample size. If, during the study conduct, the drop out rate is higher than projected, recruitment may continue until the required number of patients complete treatment.

A log of all patients enrolled into the trial (i.e. who have signed informed consent) will be maintained in the Investigator Site File (ISF) irrespective of whether they have been treated with investigational drug or not.

The investigator will make every effort to avoid the inclusion of a patient who does not meet all the inclusion criteria and/or meets at least one exclusion criterion. Should such an error nevertheless occur, this patient might be immediately excluded from the clinical trial based on individual benefit-risk assessment by the investigator. The sponsor or delegate will be informed as soon as possible.

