7.5 DETERMINATION OF SAMPLE SIZE

The sample size calculation is conducted assuming effect size of BI 690517 versus placebo, (0, 0.10, 0.20, 0.35) for (placebo, BI 690517 3 mg, BI 690517 10 mg, BI 690517 20 mg total daily dose) in log transformed UACR measured in morning void urine after 14 weeks of trial treatment from baseline. The pre-specified models in [Figure 7.5: 1](#) are used for testing null hypothesis. The following models have been selected as the candidate set of possible dose response patterns based on current expectation. Assuming the following dose groups will be tested: placebo, active BI 690517 3 mg, 10 mg, and 20 mg in terms of total daily dose.

Emax: 80% of the maximum effect is achieved at 10 mg.

Exponential: 15% of the maximum effect is achieved at 10 mg.

Linear: No assumption is needed.

[figure not shown]

Figure 7.5: 1 Shape of the considered dose response patterns for the MCPMod analysis (dose reflects planned daily dose)

In a scenario with assumed effect of (0, 0.10, 0.20, 0.35) in log (UACR) change from baseline after 14 weeks in the Treatment Period (placebo, BI 690517 3 mg, BI 690517 10 mg, BI 690517 20 mg), the trial will have 89.7% power to detect a non-flat curve using MCPMod considering one-sided 5% alpha with sample size of 60 patients per treatment arm (in patients randomised to placebo during the run-in period).

In a scenario with assumed effect of (0, 0.10, 0.16, 0.22) in log (UACR) change from baseline after 14 weeks in the Treatment Period (placebo, BI 690517 3 mg, BI 690517 10 mg, BI 690517 20 mg), the trial will have 83.1% power to detect a non-flat curve using MCPMod considering one-sided 5% alpha with sample size of 120 patients per treatment arm (all patients combined).

The sample size/power calculation were determined based on 10,000 simulations for the scenario using R4.0.2. To achieve 60 patients per group (480 total patients), 552 patients will be randomised during the Run-in period to account for a dropout rate of at most 15% before the second randomisation. A one-sided alpha of 5% will be used to keep the sample size reasonably low in this Phase 2 trial.

8. INFORMED CONSENT, TRIAL RECORDS, DATA PROTECTION, PUBLICATION POLICY, AND ADMINISTRATIVE STRUCTURE

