6.6.2 Efficacy data

6.6.2.1 Primary endpoint

Missing data for primary analysis will not be imputed:

- If some UACR value(s) at baseline is (/are) missing, all other available UACR samples in week -2, -1, and 0 will be used to derive UACR at baseline.
- If any UACR value after randomisation to the Treatment Period is missing, the missing UACR will not be imputed.
- UACR values excluded from the primary analysis according to the ICEs handling rules will not be imputed.

The Mixed-effect Model for Repeated Measures (MMRM) approach used for the primary endpoint (see [Section 7.4.1](#)) allows for missing data, assuming missing data following the "missing at random" assumption. Even patients with only one post-baseline assessment can be included in the model and can, therefore, contribute to the variance estimation. This primary analysis assumes that patients who had ICE(s) should have behaved similarly to those who remained in the study, and therefore is analogous to the hypothetical estimand strategy.

The table below describes how/when to derive UACR values for the statistical analysis:

Table 6.6.2.1: 1 Principal rule of First Morning Void (FMV) UACR derivation for analysis

	FMV UACR at baseline	FMV UACR at visit 8	FMV UACR at visit 9	FMV UACR at EoT
Derivation	Baseline FMV UACR is defined as the mean of all non-missing assessments from week -2 until prior to the first intake of trial medication BI 690517 or placebo in the Treatment Period.	Average of all available FMV UACR measured at visit 8 (week 6)	Average of all available FMV UACR measured at visit 9 (week 10)	EoT FMV UACR is defined as the mean of all non-missing assessments from week 12 to week 14 (EoT visit)

Sensitivity analyses will be conducted to investigate the potential effect of ICE handling approaches on the results of the primary analysis. Details about implementation of the sensitivity statistical analyses are described in [Section 7.4](#).

[figure not shown]

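### At the plan's own ceiling of 15% run-in dropout, 552 randomised patients leave about 469, not the 480 required, and no allowance is stated for loss in the Treatment Period

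*Protocol*

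**What the plan says.** Protocol section 7.5 sets the number to be randomised at the first randomisation, with a target of 480 patients (60 in each group), and gives the reason for the excess over 480: "552 patients will be randomised during the Run-in period to account for a dropout rate of at most 15% before the second randomisation". The same section bases its two power statements on 60 per arm (89.7%, placebo background) and 120 per arm (83.1%, both backgrounds combined).

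Two other places describe the same 480 as completers. The synopsis asks for "A minimum of 60 patients completed per arm in the Treatment Period, overall 480 completed patients". Section 3.3 says: "A minimum of 552 patients will be randomised to the Run-in Period to ensure that at least 480 will complete the study treatment". Section 3.3 also has a top-up clause: "If, during the study conduct, the drop out rate is higher than projected, recruitment may continue until the required number of patients complete treatment".

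Neither document gives a rate for loss during the 14-week Treatment Period.

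**The concern.** There are two separate problems.

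1. **The inflation step.** Dropout is a fraction of those who enter. To keep 480 after losing 15%, one divides 480 by 0.85. The stated 552 is what one gets by multiplying 480 by 1.15, and it falls short at the rate quoted.
2. **The meaning of the 480.** In section 7.5 the whole allowance is used up before the second randomisation, so its 480 are patients entering the Treatment Period. In the synopsis and section 3.3 they are patients finishing it. The two agree only if nobody is lost over 14 weeks.

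At stake are the 60 and 120 per arm on which both stated powers rest, the number to be expected at week 14, and the count against which the top-up clause is to be judged.

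**Working it through.** **Inputs (protocol section 7.5):** target 480 = 8 × 60; run-in dropout at most 15%; 552 randomised to the run-in; one-sided alpha 5%; effects on log UACR of (0, 0.10, 0.20, 0.35) at 60 per arm and (0, 0.10, 0.16, 0.22) at 120 per arm; Emax, exponential and linear candidate models.

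**Reproducing the plan's figure**

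- 480 × (1 + 0.15) = 552.0, an exact match. The protocol does not show the step, so the multiplication is inferred. The yield check below does not depend on that inference.

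**Yield and requirement**

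- Yield at 15%: 552 × (1 − 0.15) = 469.2, or 469.2/8 = 58.65 per arm (117.3 per dose with backgrounds combined).
- Shortfall: 480 − 469.2 = 10.8, about 11 patients; 10.8/480 = 2.25%.
- Number needed at 15%: 480/0.85 = 564.7, so 565, which is 13 more than 552.
- Largest loss that 552 covers: 1 − 480/552 = 13.04%.

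**If the 480 are completers.** The loss that 552 can absorb after the second randomisation, given run-in loss r, is 1 − 480/(552 × (1 − r)).

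| Run-in loss r | Entering the Treatment Period | Later loss that still leaves 480 |
|---|---|---|
| 5% | 524.4 | 8.5% |
| 10% | 496.8 | 3.4% |
| 12% | 485.8 | 1.2% |
| 15% | 469.2 | none (already short) |

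**Effect on power**

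The protocol states no standard deviation, so one was back-solved for each scenario to reproduce the stated power.

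- Model shapes: Emax with ED50 = 10 × 0.2/0.8 = 2.5 mg; exponential with delta 5.765, which puts 15% of the 20 mg effect at 10 mg; linear.
- Test: maximum of the three optimal-contrast statistics, normal critical value about 1.92.
- Back-solved SD: 0.667 (89.7% at 60 per arm) and 0.656 (83.1% at 120 per arm).

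| Patients | Per arm / per dose combined | Scenario 1 | Scenario 2 |
|---|---|---|---|
| 480 (as stated) | 60 / 120 | 89.7% | 83.1% |
| 469 (15% run-in loss) | 58.65 / 117.3 | 89.1% | 82.3% |
| 446 (a further 5%, assumed) | 55.7 / 111.4 | 87.7% | 80.6% |
| 422 (a further 10%, assumed) | 52.8 / 105.6 | 86.0% | 78.6% |

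Only the 469 row uses the plan's own dropout figure. The last two rows assume a later loss that the documents do not give, ignore partial data and allow no top-up. They are therefore upper bounds on the drop in power.

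**The case against.** The strongest reply concerns weight rather than arithmetic.

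- **The provable effect is small.** The stated powers come from 10,000 simulations, with standard errors of √(0.897 × 0.103/10,000) = 0.30 points and √(0.831 × 0.169/10,000) = 0.37 points. Losses of 0.6 and 0.8 points are about the size of a 95% margin on those estimates, and both scenarios stay above 80%. This stands.
- **The power reconstruction is approximate.** No single SD reproduces both stated powers: at 0.66 they come out near 90.3% and 82.7%. The two back-solved SDs differ by the equivalent of about 3% in sample size, since (0.667/0.656)² is about 1.03, which is more than the 2.25% shortfall. This stands as a limit on the power figures. It does not touch the head count.
- **15% is a ceiling and 552 a floor, with a top-up available.** Any run-in loss up to 13.0% yields 480 at the second randomisation, and recruitment may run past 552. But an allowance for a ceiling should hold at the ceiling. The top-up is optional and, as worded, applies when "the drop out rate is higher than projected, recruitment may continue until the required number of patients complete treatment"; the shortfall already arises at the projected 15%.
- **Completers are not the analysis count.** SAP section 6.6.2.1 notes that "Even patients with only one post-baseline assessment can be included in the model". This stands for loss after the second randomisation and is why the 446 and 422 rows overstate the drop. It does not help with patients lost in the run-in, who never reach the second randomisation.
- **The 480 are plainly completers.** The synopsis and section 3.3 do say so, and section 7.5 offers no explicit rival definition. But then section 7.5 has no allowance for the 14 weeks in which completion is decided.

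**Conclusion.** The point holds. Section 7.5 is wrong as written: 552 does not deliver 60 per group at the dropout rate it names, and it is sufficient only up to a 13.0% loss. The 480 are used in two senses, and no Treatment Period loss is stated under either.

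The size is modest. From the plan's own figures the shortfall is 11 patients (2.25%). The power cost is 0.6 to 0.8 points, conditional on the inferred SDs of 0.667 and 0.656. The one figure below 80% (78.6%) needs an assumed 10% later loss, no use of partial data and no top-up, and should not be read as a forecast. The correction should be made because a sample-size statement ought to meet its own target and because it costs almost nothing.

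**What to change.** - Define the 480 once, either as patients randomised at the second randomisation or as treatment completers, and use that definition in section 7.5, section 3.3 and the synopsis.
- In section 7.5, say either that 552 covers a total loss of 13%, or that at 15% run-in loss it yields about 469 patients (58 to 59 per arm).
- State the assumed Treatment Period loss as a number, and restate power at the sample size this implies.
- Reword the top-up clause so that it is judged against the chosen count.

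This is a change of wording and needs no extra patients; the stated power at the 15% ceiling becomes 0.6 to 0.8 points less favourable. Only if the sponsor prefers to keep 480 at the second randomisation with 15% run-in loss does the minimum rise, from 552 to 565 (13 patients).

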8.1 TRIAL APPROVAL, PATIENT INFORMATION, INFORMED CONSENT

This trial will be initiated only after all required legal documentation has been reviewed and approved by the respective Institutional Review Board (IRB) / Independent Ethics Committee (IEC) and competent authority (CA) according to national and international regulations. The same applies for the implementation of changes introduced by amendments.

Prior to patient participation in the trial, written informed consent must be obtained from each patient (or the patient’s legally accepted representative) according to ICH-GCP and to the regulatory and legal requirements of the participating country. Each signature must be personally dated by each signatory and the informed consent and any additional patient-information form retained by the investigator as part of the trial records. A signed copy of the informed consent and any additional patient information must be given to each patient or the patient’s legally accepted representative.

The investigator or delegate must give a full explanation to trial patients based on the patient information form. A language understandable to the patient should be chosen, technical terms and expressions avoided, if possible.

The patient must be given sufficient time to consider participation in the trial. The investigator or delegate obtains written consent of the patient's own free will with the informed consent form after confirming that the patient understands the contents. The investigator or [REDACTED] delegate must sign (or place a seal on) and date the informed consent form. If a trial collaborator has given a supplementary explanation, the trial collaborator also signs (or places a seal on) and dates the informed consent.

Re-consenting may become necessary when new relevant information becomes available and should be conducted according to the sponsor's instructions.

The consent and re-consenting process should be properly documented in the source documentation.

8.2 DATA QUALITY ASSURANCE

A risk-based approach is used for trial quality management. It is initiated by the assessment of critical data and processes for trial participant protection and reliability of the results as well as identification and assessment of associated risks. An Integrated Quality and Risk Management Plan or alternative plan, in line with the guidance provided by ICH Q9 and ICH-GCP E6, documents the rationale and strategies for risk management during trial conduct including monitoring approaches, vendor management and other processes focusing on areas of greatest risk.

Continuous risk review and assessment may lead to adjustments in trial conduct, trial design or monitoring approaches.

A quality assurance audit / inspection of this trial may be conducted by the sponsor, sponsor's designees, or by IRB / IEC or by regulatory authorities. The quality assurance auditor will have access to all medical records, the investigator's trial-related files and correspondence, and the informed consent documentation of this clinical trial.

8.3 RECORDS

CRFs for individual patients will be provided by the sponsor. See [section 4.1.5.2](#) for rules about emergency code breaks. For drug accountability, refer to [section 4.1.8](#).

8.3.1 Source documents

In accordance with regulatory requirements, the investigator should prepare and maintain adequate and accurate source documents and trial records that include all observations and other data pertinent to the investigation on each trial patient. Source data as well as reported data should follow the "ALCOA principles" and be attributable, legible, contemporaneous, original and accurate. Changes to the data should be traceable (audit trail).

Data reported on the CRF must be consistent with the source data or the discrepancies must be explained.

The current medical history of the patient may not be sufficient to confirm eligibility for the trial and the investigator may need to request previous medical histories and evidence of any diagnostic tests. In this case, the investigator must make at least one documented attempt to retrieve previous medical records. If this fails, a verbal history from the patient, documented in their medical records, would be acceptable.

If the patient is not compliant with the protocol, any corrective action e.g. re-training must be documented in the patient file.

For the CRF, data must be derived from source documents, for example:

- Patient identification: sex, year of birth (in accordance with local laws and regulations)
- Patient participation in the trial (substance, trial number, patient number, date patient was informed)
- Dates of patient's visits, including dispensing of trial medication
- Medical history (including trial indication and concomitant diseases, if applicable)
- Medication history
- Adverse events and outcome events (onset date (mandatory), and end date (if available))
- Serious adverse events (onset date (mandatory), and end date (if available))
- Concomitant therapy (start date, changes)
- Originals or copies of laboratory results and other imaging or testing results, with proper documented medical evaluation (in validated electronic format, if available)
- Completion of patient's participation in the trial" (end date; in case of premature discontinuation document the reason for it).
- Prior to allocation of a patient to a treatment into a clinical trial, there must be documented evidence in the source data (e.g. medical records) that the trial participant meets all inclusion criteria and does not meet any exclusion criteria. The absence of records (either medical records, verbal documented feedback of the patient or testing conducted specific for a protocol) to support inclusion / exclusion criteria does not make the patient eligible for the clinical trial.
- ECG results (original and copies of printouts)
- Source documentation for telemedicine visits
- Source documentation for visits performed at the patient's home
- Historical kidney-related data

8.3.2 Direct access to source data and documents

The investigator / institution will allow site trial-related monitoring, audits, IRB / IEC review and regulatory inspections. Direct access must be provided to the CRF and all source documents / data, including progress notes, copies of laboratory and medical test results, which must be available at all times for review by the CRA, auditor and regulatory inspector (e.g. FDA). They may review all CRFs and informed consents. The accuracy of the data will be verified by direct comparison with the source documents described in [section 8.3.1](#). The sponsor or delegate will also monitor compliance with the protocol and GCP.

In the event of force majeure or other disrupting circumstances (e.g. pandemic, war, please see [section 6](#)), site access may be restricted thus limiting the ability to perform standard site monitoring activities on site such as on-site source data review and source data verification. Therefore, some of these activities may be performed remotely or replaced by centralised monitoring to the extent possible, based on a documented risk assessment and in alignment with local regulations.

8.3.3 Storage period of records

Trial site(s):

The trial site(s) must retain the source and essential documents (including ISF) according to contract or the local requirements valid at the time of the end of the trial (whatever is longer).

Sponsor:

The sponsor must retain the essential documents according to the sponsor's SOPs.

8.4 EXPEDITED REPORTING OF ADVERSE EVENTS

BI is responsible to fulfil their legal and regulatory reporting obligation in accordance with regulatory requirements.

8.5 STATEMENT OF CONFIDENTIALITY AND PATIENT PRIVACY

Data protection and data security measures are implemented for the collection, storage and processing of patient data in accordance with the principles 7 and 12 of the World Health Organisation (WHO) GCP handbook.

Individual patient data obtained as a result of this trial is considered confidential and disclosure to third parties is prohibited with the following exceptions:

Personalised treatment data may be given to the patient's personal physician or to other appropriate medical personnel responsible for the patient's welfare. Data generated at the site as a result of the trial need to be available for inspection on request by the participating physicians, the sponsor's representatives, by the IRB / IEC and the regulatory authorities.

